5.2 Number of Participants

Approximately 250 participants will be randomized (226 to Arm A and B, and 24 in Arm C).

It is estimated that approximately 357 enrolled participants will be needed to achieve these 250 randomized.

5.3 End of Study Definition

The start of the study is defined as first participant screened. End of study is defined as the end of the survival follow-up period for the last participant. Study completion is defined as the final date on which data for the primary endpoint was or is expected to be collected, if this is not the same.

Additional follow-up for OS may be conducted up to approximately 5 years after the randomization of the last participant.

5.4 Scientific Rationale for Study Design

Preliminary efficacy was seen with a lower dose of relatlimab and nivolumab combination in a single-arm study. [REDACTED]

To further evaluate and understand these data, this study aims to:

- Understand the added benefit of relatlimab to nivolumab monotherapy.
- [REDACTED]

5.4.1 Rationale for Choice of Comparators

[figure not shown]
Nivolumab was chosen to be the comparator treatment to explore efficacy in 2L and subsequent settings. Nivolumab initially received accelerated approval for use in HCC patients who have failed sorafenib treatment.¹⁴ Currently, the National Comprehensive Cancer Network (NCCN) guidelines recommend nivolumab in subsequent lines of therapy in certain circumstances.³⁴

5.4.2 Rationale for Use of Relatlimab in Combination with Nivolumab

Several studies conducted and consequent approvals of immunotherapy agents support the use of immunotherapies in HCC, as previously described. HCC is a primary liver tumor that typically develops a pattern of chronic liver disease, particularly in patients with cirrhosis or chronic viral infection. The viral association makes it suitable for combination therapy BMS-986016 (relatlimab) and nivolumab. On one hand, it has been shown that LAG-3 is selectively up-regulated on tumor infiltrating CD8+ T cells and that HBV-specific CD8+ tumor-infiltrating lymphocytes (TILs) have an impaired effector function in participants with HCC.⁴⁹ [REDACTED]

Besides the already proven benefit of immunotherapies in HCC, [REDACTED] Phase 1/2 studies are supporting the efficacy of LAG-3 mechanism of action in HCC. Lymphocytic infiltration of the tumor and a high CD4+:CD8+ T-cell ratio have been associated with reduced risk of tumor recurrence following liver transplantation for HCC.⁵⁰ Adoptive immunotherapy with autologous lymphocytes activated with recombinant-2 and antibody to CD3 in patients who had undergone curative resection resulted in significantly longer recurrence-free and disease-specific survival, although OS did not differ significantly between treated and control groups.⁵¹ The data nonetheless imply a central role of T cells in modulating tumor progression and provide strong justification for T-cell immunotherapy.²⁰ There is also evidence that FGL-1, a liver-secreted protein, is a major LAG-3 functional ligand independent from MHC-II. FGL-1 inhibits antigen-specific T-cell activation, and ablation of FGL-1 in mice promotes T-cell immunity. Blockade of the FGL-1:LAG-3 interaction by monoclonal antibodies stimulates tumor immunity and is therapeutic against established mouse tumors in a receptor-ligand, inter-dependent manner. FGL-

1 is highly produced by human cancer cells, and elevated FGL-1 in the plasma of cancer patients is associated with a poor prognosis and resistance to anti-PD-1/B7-H1 therapy.⁵²

5.4.3 Rationale for Duration of Treatment

All participants will be treated until progression or appearance of intolerable toxicities, or if confirmed CR is achieved. Continuous tumor assessment every 8 weeks and safety evaluation will guide the decision to treat a participant with additional cycles of study therapy if the participant has confirmed clinical benefit.

Tumor assessments should continue until disease progression or treatment discontinuation, whichever occurs later. Participants with unconfirmed progressive disease, SD, or PR at the end of a given cycle will continue to the next treatment cycle.

Individual participants with confirmed CR will be given the option to discontinue study therapy on a case-by-case basis, after specific consultation and agreement between the Investigator and BMS Medical Monitor, in settings where benefit/risk justifies discontinuation of study therapy.

Participants will be allowed to continue study treatment until the first occurrence of any of the following situations:

- Progressive disease defined by RECIST v1.1, unless participants meet criteria for treatment beyond progression (see [Section 8.1.2](#)).
- Clinical deterioration suggesting that no further benefit from treatment is likely.
- Intolerability to therapy.
- Participant meets criteria for discontinuation of study treatment.

5.4.4 Rationale for Stratification Factors

Stratification will occur by:

- Region (Asia [excluding Japan] vs rest of the world [including Japan])
- MVI/EHS (yes or no)
- LAG-3 expression 

Recent pivotal studies in this indication and line/setting of therapy used the following stratification factors: the CA209040 study that led to the approval in 2L stratified by HCC HCV vs non-HCV and presence of Investigator-assessed vascular invasion (VI) or EHS vs absence of VI/EHS; while the KEYNOTE-240 study, which did not meet its endpoints with pembrolizumab monotherapy

approval, stratified by geographic region (Asia excluding Japan, vs non-Asia including Japan), MVI (yes or no) and AFP (< 200 ng/mL vs > 200 ng/mL).

A number of randomized Phase 3 trials in HCC that followed the sorafenib pivotal trials have failed to demonstrate positive outcomes. These include 4 Phase 3 trials in the 1L setting with sunitinib, brivanib, linifanib, and erlotinib.^{53, 54, 55, 56} The reasons for trial failure are considered heterogeneous and include lack of understanding of critical drivers of tumor progression/dissemination, liver toxicity, flaws in trial design, or marginal antitumor potency.⁵⁷ With respect to trial design, publications have cited potential imbalances in prognostic baseline factors.

[figure not shown]
The randomized Phase 3 trials were mostly stratified by the presence or absence of VI and/or EHS, geographic region, and Eastern Cooperative Oncology Group (ECOG) performance status. Despite stratification and randomization, notable differences were observed in the outcomes. Subset analysis of the 2 pivotal sorafenib trials showed differences in the outcomes of participants who had VI/EHS compared to those who did not have VI/EHS. Participants who had VI/EHS had worse outcomes than participants without VI/EHS.^{58, 59} This study will therefore stratify by VI/EHS.

The impact of differing HCC patient populations and different approaches to clinical practice in the different regions is still important to consider. Based on pivotal trial results, differences in outcome are also captured in outcome by infectious vs non-infectious etiology. Based on World Health Organization (WHO) data, the prevalence of HCV is highest in the eastern Mediterranean region (>2%),⁶⁰ and HBV prevalence is 2-7% in Mediterranean countries, Japan, central Asia, the Middle East, and parts of South America.⁶¹ These regions where HBV and HCV infection and consequent HCC is prevalent are in the Asian region. The Japanese HCC population is different from the other non-Japanese Asian HCC populations, with a higher prevalence of HCV-HCC and a better screening system. The KEYNOTE-224 and IMbrave 150 studies stratified by region, including Japan to the rest of the world.⁶² Therefore, this study will not stratify by etiology, assuming the majority of HCC with infectious origin comes from the Asian countries. This study will therefore stratify by region.

[figure not shown]
[REDACTED]

[REDACTED] To balance the expression across arms, LAG-3 will also be treated as a stratification factor.

[REDACTED]

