2D-Echocardiogram	X		LVEF assessment with documented LVEF \geq 50% by either TTE (preferred test) or MUGA scan within 6 months from first study drug administration. If more than 1 scan is performed, the most recent scan is applicable.
12-lead ECG		X	12-lead ECGs should be recorded after the participant has been supine for at least 5 minutes. ECGs must be collected and assessed using the site's own ECG machine.
Chest Radiograph	X		Posterior-anterior and lateral (either side) chest x-ray to establish baseline.
Serious Adverse Events Assessment	X		SAEs collected from time of consent (pre-screening and/or main ICF). All AEs (SAEs or non-serious AEs) associated with SARS-CoV-2 infection collected from time of consent. See Section 9.2 . AEs are graded per CTCAE v5, except as described for hepatic and endocrinopathies [REDACTED].
Laboratory Tests		X	Local laboratory testing, including testing for symptomatic SARS-CoV-2 infection. Hematology, serum chemistry, and urinalysis, as outlined in Section 9.4.4 .
Urinalysis		X	See Section 9.4.4 .
Thyroid Function Tests		X	See Section 9.4.4 .
Serology	X		Hep B surface antigen, Hep B surface antibody, Hep B core antibody, Hep B DNA viral load (PCR), Hep C RNA viral load (PCR), Hep C antibody, and Hep D antibody (if chronic HBV infection). See Section 9.4.4 .

Table 2-1: Screening Procedural Outline (CA224073)

Procedure	Screening Visit -28 Days	Day -14 to Day -1 Visits	Notes ^a (All windows are based on calendar days.)
			HIV (when required by local regulations [see Appendix 7]), must be done at local laboratory within 28 days prior to randomization. See Section 9.4.4 .
Coagulation Profile	X		Including PT/INR and aPTT. If screening laboratory test samples are drawn within 4 days of first treatment, then these laboratory samples will also qualify as Day 1 (predose) laboratory samples. See Section 9.4.4 .
Disease Assessment: Serum Alpha-fetoprotein	X		See Section 9.4.4 .
Pregnancy Test (WOCBP only)	X		Local laboratory testing Serum or urine (minimum sensitivity equivalent units 25 IU/L or equivalent units of HCG) to be done at screening visit and repeated within 1 day prior to first dose of study treatment. An extension up to 72 hours prior to the start of study treatment is permissible in situations where results cannot be obtained within the standard 24-hour window.

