10.3.1 Efficacy Analyses

Efficacy Analyses are described in [Table 10.3.1-1](#) and will be performed on the randomized population. If Arm C is closed or dropped and number of participants randomized in Arm C is small, the primary efficacy comparison will be performed between Arm B vs Arm A and the efficacy analysis in Arm C will be descriptive.

Table 10.3.1-1: Efficacy Analyses

Endpoint	Statistical Analysis Methods
Primary	The difference in ORR between relatlimab in combination with nivolumab (Arm B) vs nivolumab (Arm A) will be presented by BICR using RECIST v1.1 computed using a simple proportion and 95% Clopper-Pearson confidence interval for this study. In addition, posterior probability of the true difference of ORR assessed by BICR using RECIST v1.1 to fall in the activity interval given the data will be provided. Also, the posterior mean of the difference of ORR between the two arms and the corresponding 90% credible intervals will also be provided. The efficacy analysis in Arm C will be descriptive.
Secondary	ORR assessed by Investigator and DCR will be computed and analyzed using frequency statistics. DOR, PFS, and OS will be analyzed using the Kaplan-Meier method.

Abbreviations: BICR = Blinded Independent Central Review; DCR = disease control rate; DOR = duration of response; LAG-3 = lymphocyte activation gene 3; OS = overall survival; PFS = progression-free survival; ORR = objective response rate; RECIST = Response Evaluation Criteria in Solid Tumors.

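### Region is only a partial proxy for etiology, and no visible analysis adjusts for etiology, AFP or the stratification factors (minor)

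*Combined protocol and SAP*

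**What the plan says.** Section 5.4.4 names three stratification factors: region (Asia without Japan against the rest of the world with Japan), macrovascular invasion or extrahepatic spread, and LAG-3 expression. On etiology it states: "Based on pivotal trial results, differences in outcome are also captured in outcome by infectious vs non-infectious etiology". It gives HCV prevalence as highest, above 2%, in the eastern Mediterranean. For HBV it says: "HBV prevalence is 2-7% in Mediterranean countries, Japan, central Asia, the Middle East, and parts of South America". It concludes: "These regions where HBV and HCV infection and consequent HCC is prevalent are in the Asian region". From this it draws the decision: "Therefore, this study will not stratify by etiology, assuming the majority of HCC with infectious origin comes from the Asian countries".

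The same section describes Japan as having more HCV-related HCC than other Asian populations. It also reports how two cited trials stratified: the second-line nivolumab study by HCV status, and KEYNOTE-240 by AFP.

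Table 2-1 (Section 2) schedules a full hepatitis B and C serology panel at screening, and a row headed "Disease Assessment: Serum Alpha-fetoprotein". Inclusion criterion 2 m (Section 6.1) defines HBV-related, HCV-related and non-viral HCC.

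Table 10.3.1-1 gives the primary analysis as the Arm B versus Arm A difference in ORR from simple proportions, with posterior summaries. The other response endpoints get frequency statistics; duration of response, PFS and OS get Kaplan-Meier. No covariate or stratum is mentioned.

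**The concern.** Two things do not fit together. First, the argument for using region in place of etiology rests on the claim that the high-prevalence areas are Asian, but the list it refers to includes areas that are not. It also includes Japan, which the trial's own factor assigns to the other stratum. The rest-of-world stratum is therefore likely to be mixed in etiology on the protocol's own evidence.

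Second, a factor that the protocol links to outcome is left out of randomization, and the visible analysis does not make up for that. Section 5.4.4 itself recalls that imbalance in prognostic baseline factors has been cited as a possible reason for failed HCC trials. The data needed for adjustment are already collected.

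What is at stake is precision, and how readily a reader can set aside chance imbalance as an explanation. It is not the validity of the randomized comparison.

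**Working it through.** The plan gives no figure on this point to reproduce. The steps below size the issue.

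**Inputs.** From the documents: 226 participants in Arms A and B (Section 5.2), taken as 113 per arm, and nivolumab ORR of 14% (Section 1). Assumed: factor prevalence, ORR gap between factor levels, etiology mix by region, an ORR of 25% in Arm B for one case, and the hazard ratios. The earlier 2:1:2 allocation would make the split roughly 119 to 107, which changes these results negligibly.

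**1. Chance imbalance without stratification.** The standard deviation of the between-arm difference in prevalence q is √(2q(1−q)/113). At q = 0.40 this is √(0.48/113) = 6.5 points. The exact probability, from two Binomial(113, q) counts, of a difference of at least 10 points is 11.8% at q = 0.40. It runs from 9.5% (q = 0.30 or 0.70) to 12.6% (q = 0.50).

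**2. What region stratification removes.** With half of participants in each region and infectious shares a and r, the within-region variance is w = 0.5a(1−a) + 0.5r(1−r). The fraction left uncontrolled is w/[q(1−q)], with q = (a+r)/2. The chance of a 10-point imbalance uses the normal approximation with SD √(2w/113).

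| Infectious share, Asia / rest of world (assumed) | w | q(1−q) | Left uncontrolled | Chance of ≥10 points |
|---|---|---|---|---|
| 80% / 20% | 0.160 | 0.250 | 64% | 6% |
| 80% / 50% | 0.205 | 0.2275 | 90% | 10% |
| 70% / 50% | 0.230 | 0.240 | 96% | 12% |

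Region helps materially only if etiology differs sharply between the strata. The documents give no etiology mix by region.

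**3. Effect on the ORR difference.** Shift = imbalance × ORR gap between factor levels. A 10-point imbalance with gaps of 5, 10 and 15 points gives shifts of 0.5, 1.0 and 1.5 points. The standard error is √(2×0.14×0.86/113) = 4.6 points at 14% in both arms, and √((0.14×0.86 + 0.25×0.75)/113) = 5.2 points at 14% against 25%.

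**4. Precision gained for ORR.** For a factor of 50% prevalence with ORR gap d, the share of variance explained is 0.25d²/(0.14×0.86). At d = 0.05, 0.10 and 0.15 this is 0.5%, 2.1% and 4.7%, so the standard error falls by 0.3%, 1.0% and 2.4%. Simulation of the adjusted difference under assumed effects gave reductions of about 1% to 4%, without bias. Overall, roughly 0% to 4%.

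**5. PFS and OS.** Simulated trials of 226 with a true treatment HR of 0.70, analysed by a Cox model with and without the factor (2,000 trials):

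| Factor HR (assumed) | Power unadjusted | Power adjusted | Gain, points |
|---|---|---|---|
| 1.5 | 65.4% | 66.3% | 0.9 |
| 2.0 | 62.2% | 67.2% | 5.0 |
| 2.5 | 56.7% | 68.1% | 11.4 |

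A second simulation (800 trials, about 200 events) agreed: 63% to 70% at a factor HR of 2.0 and 60% to 69% at 2.5. The visible plan states no event count, Cox model or test, so these gains are illustrative.

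**6. Why not add strata.** If each factor has two levels, the present design has 8 cells, about 28 participants each. Adding etiology gives 16 (about 14 each), and AFP as well gives 32 (about 7 each). Adjustment in the analysis is the more proportionate route.

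**The case against.** The sponsor has a fair case. Section 3.2 says HCC incidence varies geographically largely because of HBV and HCV, which supports region as a partial proxy. A majority of infectious cases can come from Asia even when some come from elsewhere, and Section 5.4.4 reports population prevalence, not the mix of enrolled participants. Section 3.2 also reports nivolumab activity whatever the etiology, which weakens the case that etiology drives ORR. These points stand, and they are why region is called a partial proxy here rather than a failed one. The activity statement does not, however, show that etiology is unrelated to PFS, OS or the added effect of relatlimab, and Section 5.4.2 itself ties the rationale for the combination to viral association.

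A reader might infer more than the documents support:

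- That the protocol treats AFP as prognostic. It does not. AFP appears as a stratifier in one cited trial, a selection criterion in another, and a laboratory test.
- That etiology and AFP are absent from every analysis. Parts of Section 10 are redacted, Section 10.3 calls its text a summary, and the SAP is to follow. Only the absence of any visible use can be stated.
- That a chance imbalance could not be told apart from a treatment effect. Randomization keeps the comparison unbiased, the interval already allows for chance imbalance, and factors measured at screening can be compared between arms.
- That the simulated unadjusted hazard ratios, averaging 0.716 to 0.729 against a true 0.70 at factor HRs of 2.0 to 2.5, show harm from imbalance. They reflect the difference between conditional and unadjusted hazard ratios (non-collapsibility).

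**Conclusion.** The point holds as a minor one. The stated reason for not stratifying by etiology conflicts with the regional data in the same paragraph and with Japan's place in the region factor. Region therefore balances etiology only partly, and by how much cannot be determined. No visible analysis uses etiology, AFP or the stratification factors.

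For the primary endpoint the practical effect is small: a plausible imbalance moves the ORR difference by a fraction of its standard error, and adjustment sharpens it only slightly. For PFS and OS the gain ranges from negligible to about 11 points of power, depending entirely on how prognostic the factors turn out to be, which the documents do not say. The primary conclusion is not at risk. All sizes rest on 113 per arm and on the assumed prevalences, ORR gaps and hazard ratios shown.

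**What to change.** Correct the etiology paragraph in Section 5.4.4: say that region is a partial proxy, drop the statement that all the listed areas are Asian, and check the claim there that KEYNOTE-224 stratified by region. Section 3.1 describes that study only as 104 participants treated with pembrolizumab, while Section 5.4.4 separately describes KEYNOTE-240 as region-stratified.

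In the SAP, prespecify beside the unadjusted results:

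- **ORR:** a standardized risk difference with 95% CI from a logistic model containing treatment, the three stratification factors, viral versus non-viral etiology (as defined in inclusion criterion 2 m) and log baseline AFP.
- **PFS and OS:** a Cox model stratified by the randomization factors, with etiology and log AFP as covariates.

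If such analyses already exist in redacted text or the SAP, it is enough to confirm them. The unadjusted difference and the posterior summaries stay as they are, and randomization does not change.

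The cost is wording, a rule for missing AFP, and a logistic model with about six terms on few responders: 226 × 0.14 ≈ 32 at an ORR of 14%, or 226 × 0.20 ≈ 45 at an assumed 20%. That is workable for a supporting estimate, but is a reason to keep the covariate list short.

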5.5 Justification for Dose

5.5.1 Justification for Nivolumab Dose

[figure not shown]
Nivolumab 480 mg Q4W has been approved in Europe for use as monotherapy in patients with melanoma and renal cell carcinoma (RCC) and in the US for use as monotherapy in patients with melanoma, RCC, non-small cell lung cancer (NSCLC), and other indications, including HCC.

The nivolumab dose of 480 mg Q4W was selected based on clinical data and modeling and simulation approaches using population PK (PPK) and exposure-response (E-R) analyses of data from studies in multiple tumor types (melanoma, NSCLC, RCC, squamous cell carcinoma of the head and neck [SCCHN], urothelial carcinoma [UC], and classical Hodgkin lymphoma [cHL]), where body weight-normalized dosing (mg/kg) has been used. The PPK analyses have shown that exposure to nivolumab increased dose proportionally over the dose range of 0.1 to 10 mg/kg administered Q2W, and no clinically meaningful differences in PK across ethnicities and tumor types were observed. Nivolumab clearance (CL) and volume of distribution were found to increase as the body weight increases, but less than proportionally with increasing weight, indicating that mg-per-kg dosing represents an over adjustment for the effect of body weight on nivolumab PK.

The PPK model previously developed using data from NSCLC participants has recently been updated, using data from 3,203 participants from 19 studies investigating nivolumab in the treatment of melanoma, NSCLC, RCC, SCCHN, UC, and cHL. In this dataset, the median (minimum - maximum) weight was 76.7 kg (34.1 kg - 180 kg) and thus, an approximately equivalent dose of 3 mg/kg Q2W for an 80-kg participant, nivolumab 480 mg Q4W was selected for future studies.

Nivolumab 480 mg Q4W is predicted to produce similar exposures to those of 3 mg/kg Q2W and 240 mg Q2W regimens. The overall distributions of nivolumab average steady state exposures are comparable after treatment with either nivolumab 3 mg/kg Q2W or nivolumab 480 mg Q4W, although the flat-dose regimen of 480 mg Q4W is predicted to result in approximately 43% higher steady-state peak concentration (C_{maxss}) and approximately 16% lower steady-state trough concentrations compared to the reference regimen of 3 mg/kg Q2W. Across the various tumor types in the clinical program, nivolumab has been shown to be safe and well tolerated up to a dose level of 10 mg/kg, and the relationship between nivolumab exposure produced by 3 mg/kg and efficacy and safety has been found to be relatively flat. Although nivolumab C_{maxss} is predicted to be higher following 480 mg Q4W, these exposures are predicted to be lower than or within the exposure ranges observed at doses up to 10 mg/kg Q2W used in the nivolumab clinical program and are not considered to put patients at increased risk. In addition, there was no difference in AE profile by body weight groups when extensive evaluations were performed with available 3 mg/kg Q2W and 10 mg/kg Q2W data. The exposures predicted following administration of nivolumab 480 mg Q4W are on the flat part of the E-R curves for previously investigated tumors (melanoma and NSCLC) and are not predicted to affect efficacy. Based on these data, nivolumab 480 mg Q4W is expected to have similar efficacy and safety profiles to nivolumab 3 mg/kg Q2W. For lower body weight patients, given the relatively flat E-R relationship of nivolumab, the increased exposures from 480 mg Q4W are not expected to pose an increased risk.

Nivolumab 480 mg Q4W is currently being evaluated in various studies across the nivolumab clinical development program. Preliminary results from pooled analyses, including 310 participants who received nivolumab 480 mg IV over 30 minutes Q4W, showed that the safety profile is consistent with the established safety profile of nivolumab (240 mg Q2W or 3 mg/kg Q2W administered IV over 60 minutes) across multiple indications, and no new safety concerns were identified. In HCC, this dose schedule is currently approved for the treatment of advanced HCC in the US and it is also under evaluation in an ongoing trial of nivolumab monotherapy in the adjuvant setting (CA2099DX). Therefore, in this study, 480 mg Q4W will be used for the nivolumab dose; this dose will provide a more convenient dosing regimen for participants, without compromising safety.

